## 12.5 Handling of Missing Data

No imputation of missing data is planned.

## 12.6 Safety Analyses

The safety endpoints are:

- Ocular and nonocular AEs and SAEs
- Device deficiencies
- Secondary surgical interventions
- Unplanned intraoperative procedures

There are no safety hypotheses planned in this study. The focus of the safety analysis will be a comprehensive descriptive assessment of occurrence of adverse events as well as the other listed parameters.

All adverse events occurring from the time a subject signs informed consent to study exit will be accounted for in the reporting. Safety analyses will be conducted using the safety analysis set on a treatment-emergent basis. Descriptive summaries (counts and percentages) and listings will be presented. Individual subject listings will be provided for AEs that occur after signing informed consent but prior to exposure to IP.

### 12.6.1 Analysis of Primary Safety Endpoint(s)

All adverse events reported to Alcon will be accounted for in the reporting. Descriptive summaries (counts and percentages) and listings will be presented. The applicable definition of an adverse event is in the study protocol. A listing of all adverse events will be constructed to provide further details.

The applicable definition of a device deficiency is in the study protocol. A frequency table showing counts for each device deficiency category will be presented. In addition, a listing of all device deficiencies will be provided.

Descriptive statistics (counts, percentages, and two-sided 95% exact binomial confidence intervals) of eyes with secondary surgical interventions (SSIs) will be presented. In addition, a listing of subjects with SSIs will be produced.

Unplanned intraoperative procedures that occur during surgery will be recorded. Descriptive statistics including the count, percentage, and a two-sided 95% exact binomial confidence interval for the percentage will be produced and will be accompanied by a listing.

## 12.7 Interim Analyses and Reporting

No interim analyses are planned.

## 12.8 Sample Size Justification

Based on a sample of 100 surgeries, the expected half-width of the 95% confidence interval for the percentage of surgeons reporting 'yes' to the question "***Did UNITY VCS using vitreoretinal or combined surgical functionality perform per the intended use as defined in protocol Section 5.1?***" will be  $1.96 \cdot \sqrt{(p(1-p)/100)}$ . This half-width is widest at  $p = 50\%$ . Under this conservative assumption, the expected half-width is < 10% given the sample size of 100.

Allow enrollment for an additional 10% for screen failure and 10% for loss to follow-up to ensure 100 completed subjects.

# 13 DATA HANDLING AND ADMINISTRATIVE REQUIREMENTS

## 13.1 Subject Confidentiality

The investigator must ensure that the subject's identity is kept confidential throughout the course of the study. In particular, the investigator must keep an enrollment log with confidential identifying information that corresponds to the subject numbers and initials of each study participant. The study sponsor may collect a copy of the enrollment log ***without any directly identifying subject information***.

The study sponsor may share patient-level data collected in this trial with qualified researchers to help facilitate product development or enhancements in research that is not directly related to the study objectives. The informed consent explains this to the study subject.

## 13.2 Completion of Source Documents and Case Report Forms

The nature and location of all source documents will be identified to ensure that original data required to complete the CRFs exist and are accessible for verification by the site monitor, and all discrepancies shall be appropriately documented via the query resolution process. Site monitors are appointed by the study sponsor and are independent of study site staff.

If electronic records are maintained, the method of verification must be determined in advance of starting the study.

At a minimum, source documents include the following information for each subject:

- Subject identification (name, sex, race/ethnicity)

- Documentation of subject eligibility
- Date of informed consent
- Dates of visits
- Documentation that protocol specific procedures were performed
- Results of study parameters, as required by the protocol
- IP accountability records
- Documentation of AEs and other safety parameters (if applicable)
- Records regarding medical histories and the use of concomitant therapies prior to and during the study
- Date of study completion and reason for early discontinuation, if applicable

It is required that the author of an entry in the source documents be identifiable. Direct access to source documentation (medical records) must be allowed for the purpose of verifying that the data recorded on the CRF are consistent with the original source data.

Only designated individuals at the site will complete the CRFs. The CRFs must be completed at regular intervals following the clinical study visit schedule. It is expected that all data reported have corresponding entries in the source documents. The principal investigator is responsible for reviewing and certifying that the CRFs are accurate and complete. The only subject identifiers recorded on the CRFs will be subject number, and subject demographic information.

### **13.3 Data Review and Clarifications**

A review of CRF data to the subject's source data will be completed by the site monitor to ensure completeness and accuracy. After the CRFs have been completed, additional data clarifications and/or additions may be needed as a result of the data cleaning process. Data clarifications are documented and are part of each subject's CRF.

### **13.4 Sponsor and Monitoring Responsibilities**

The study sponsor will select principal investigators that are qualified by education, training, and experience to assume responsibility for the proper conduct of this clinical trial. For this study, the principal investigator and sub investigators must be health care professionals appropriately licensed to perform vitreoretinal and cataract surgery.

[figure not shown]
The study sponsor is financially funding this clinical trial and will compensate the investigator and/or the institution(s) at which the study is conducted in accordance with a signed clinical trial agreement.

The study sponsor will designate a monitor to conduct the appropriate site visits at the appropriate intervals according to the study monitoring plan. The clinical investigation will be monitored to ensure that the rights and wellbeing of the subjects are protected, the reported data are accurate, complete, and verifiable from the source documents, and the study is conducted in compliance with the current approved protocol (and amendments[s], if applicable), with current GCP, and with applicable regulatory requirements.

The site may not screen subjects or perform the informed consent process on any subject until it receives a notification from an appropriate study sponsor representative that the site may commence conducting study activities. Monitoring will be conducted periodically while the clinical study is ongoing. Monitoring methods may include site visits, telephone, written, and fax correspondence. Close-out visits will take place after the last visit of the last subject at the site.

Videos of surgery should be maintained with subject records for verification as source data and sent to sponsor for review as requested. Such data will be coded with a subject number only and will not contain subject personal information.

A coordinating investigator may be identified by the study sponsor to review and endorse the final study report. In cases where a coordinating investigator is engaged, the study sponsor will select the coordinating investigator based upon their experience, qualifications, active study participation, and their willingness and availability to take on this role.

## **13.5 Regulatory Documentation and Records Retention**

The investigator is required to maintain up-to-date, complete regulatory documentation as indicated by the study sponsor and the investigator's files will be reviewed as part of the ongoing study monitoring. Financial information is to be kept separately.

Additionally, the investigator must keep study records and source documents consistent with the terms of the clinical study agreement with the study sponsor. If the investigator retires, relocates, or for any other reason withdraws from responsibility of keeping the study records, then the study sponsor must be notified, and suitable arrangements made for retention of study records and source documents needed to comply with national and international regulations.

## **13.6 Quality Assurance and Quality Control**

The study sponsor will secure agreement from all involved parties to ensure direct access to all study related sites, source data and documents, and reports for the purpose of monitoring and auditing by the study sponsor, and inspection by domestic and foreign regulatory authorities. Quality control will be applied to each stage of data handling to ensure that all data are reliable and have been processed correctly. Agreements made by the study sponsor with the investigator/institution and any other parties involved in the clinical study will be provided in writing as part of the protocol or as a separate agreement.

# **14 ETHICS**

Investigations are conducted in compliance with GCP; international and national regulations, laws and guidelines; ISO 14155:2020; the conditions of approval imposed by reviewing IRBs/IECs or regulatory authorities; and in accordance with the ethical medical research principles outlined in the Declaration of Helsinki.

- The SOPs of the study sponsor and contract research organizations participating in the conduct of the clinical study and all other applicable regulations shall apply.
- Notifications and timelines for reporting protocol deviations should be based upon applicable ethics committee requirements.

The investigator must ensure that all personnel involved in the conduct of the study are qualified to perform their assigned responsibilities through relevant education, training, and experience. The investigator and all clinical study staff must conduct the clinical study in compliance with the protocol. The investigator is not allowed to deviate from the protocol except to protect the rights, safety, and wellbeing of human subjects under emergency circumstances. Emergency deviations may proceed without prior approval of the sponsor and the IRB/IEC but shall be documented and reported to the sponsor and the IRB/EC as soon as possible. Deviations from this protocol, regulatory requirements, and/or GCP must be recorded and reported to the sponsor prior to database lock. If needed, corrective and preventive action should be identified, implemented, and documented within the study records. Failure to implement identified corrective and preventative actions may result in site closure by the sponsor. Use of waivers to deviate from the clinical protocol is prohibited.

Before clinical study initiation, this protocol, the informed consent form, if applicable, any other written information given to subjects, and any advertisements planned for subject recruitment must be approved by an IRB/IEC. The investigator must provide documentation of the IRB/IEC approval to the study sponsor. The approval must be dated and must identify the applicable protocol, amendments (if any), informed consent form, assent form (if any), all applicable recruiting materials, written information for subject, and subject compensation programs. The IRB/IEC must be provided with a copy of the investigator's brochure, any periodic safety updates, and all other information as required by local regulation and/or the IRB/IEC. Any additional requirements imposed by the EC or regulatory authority shall be followed. At the end of the study, the investigator must notify the IRB/IEC about the study's completion. The IRB/IEC also must be notified if the study is terminated prematurely. Finally, the investigator must report to the IRB/IEC on the progress of the study at intervals stipulated by the IRB/IEC.

Voluntary informed consent must be obtained in writing from every subject. The obtaining of consent shall be documented before any procedure specific to the clinical investigation is applied to the subject.

The investigator must have a defined process for obtaining the required consent. Specifically, the investigator, or their delegate, must explain the clinical study to each potential subject and the subject must indicate voluntary consent by signing and dating the approved informed consent form. The subject must be provided an opportunity to ask questions of the investigator, and if required by local regulation, other qualified personnel. The investigator must provide the subject with a copy of the consent form written in a language the subject understands. The consent document must meet all applicable local laws and provide subjects with information

regarding the purpose, procedures, requirements, and restrictions of the study, along with any known risks and potential benefits associated with the IP and the study, the available compensation, and the established provisions for maintaining confidentiality of personal, protected health information. Subjects will be told about the voluntary nature of participation in the study and must be provided with contact information for the appropriate individuals should questions or concerns arise during the study. The subject also must be told that their records may be accessed by appropriate authorities and sponsor-designated personnel. The investigator must keep the original, signed copy of the consent (file in subject's medical records) and must provide a duplicate copy to each subject according to local regulations.

The investigator must have a defined process in case a subject would like to withdraw their consent (s). The investigator is the designated contact point for any such withdrawals.

The investigator must have a defined process in case a subject would like to exercise any of their rights under applicable data protection laws. The investigator is the designated contact point for any such requests.

The study sponsor assures that the key designs of this protocol will be registered on public databases where required by current regulations, and, as applicable, results will be posted.

1 STUDY OBJECTIVES AND DESIGN

1.1 Study Objectives

The objective of this study is to obtain device-specific safety and performance clinical data to support marketability in Europe and to collect formal user feedback.

1.2 Study Description

This is a prospective, single arm, nonrandomized, multicenter study of adults with clinically documented diagnosis of vitreoretinal disease(s) with or without cataract and who meet the inclusion/exclusion criteria.

The investigational device, the UNITY VCS, is intended to facilitate management of fluid and gases, as well as removal, grasping, cutting, illumination, and coagulation of ocular materials. The target patient population for this study are those undergoing vitreoretinal surgery with or without simultaneous cataract surgery.

Planned study visits will include screening/enrollment, surgery using UNITY VCS, follow-up at 1 day, 1 week, 1 month, and 3 months. Unscheduled visit data will be included as appropriate.

The schedule of study procedures and assessments can be found in the appendix.

1.3 Randomization

Not applicable.

1.4 Masking

This is an open-label study.

1.5 Interim Analysis

No interim analyses are planned for this study.

2 ANALYSIS SETS

All eligible subjects will be screened to determine if they meet all inclusion and no exclusion criteria. Subjects who provide informed consent will be considered enrolled in the study.

2.1 Full Analysis Set

The primary analysis set for the effectiveness outcomes will be the full analysis set. The full analysis set includes all eyes with successful completion of surgery.

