# **12 ANALYSIS PLAN**

## **12.1 Subject Evaluability**

Final subject evaluability must be determined prior to locking the database, based upon the deviations and evaluability plan.

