### 12.2.2 Safety Analysis Set

The safety analysis set will include all eyes with attempted use of the UNITY VCS (successful or aborted after contact with the eye) and will be used for the safety outcomes. Attempted use of the UNITY VCS is defined as any time the device makes contact with the eye.

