#### 12.4.1.2 Analysis Methods

After each surgery, the surgeon completes a user questionnaire. For subjects in the full analysis set, the rate of 'yes' responses to the question listed above will be presented with a count and percentage and will be accompanied by a two-sided exact binomial 95% confidence interval.

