2.2 Safety Analysis Set

The safety analysis set will include all eyes with attempted use of the UNITY VCS (successful or aborted after contact with the eye) and will be used for the safety outcomes. Attempted use of the UNITY VCS is defined as any time the device makes contact with the eye.

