3 SUBJECT CHARACTERISTICS AND STUDY CONDUCT SUMMARIES

Subject characteristics and study conduct summaries will include subject disposition, demographics, and reason for surgery. Summaries will be presented for subjects in the safety and full analysis sets indicating the count receiving posterior segment (i.e., vitreoretinal) only or a combined (i.e., vitreoretinal and simultaneous cataract) procedure. Additionally, procedures will be summarized by simple and complex. Listings will be provided for medical history, screen failures by reason, protocol deviations, baseline medications, and for subjects included in the safety analysis set but excluded from the full analysis set. All descriptive summary statistics will be displayed with count and percent for categorical data such as sex, age, race, and ethnicity. Count (n), mean, standard deviation, median, minimum, and maximum will be presented for continuous variables such as age.

Subject characteristics and study conduct summaries will be presented for the full analysis set unless the safety analysis set is different, in which case they will be presented for both.

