4.3 Statistical Methods for Effectiveness Analyses

Standard descriptive statistics will be presented based on the type. Individual subject data listings will also be provided. No imputation of missing data is planned. The full analysis set will be used for all effectiveness analysis and all analyses will be based on the study eye unless otherwise stated.

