4.3.1 Analysis of the Primary Endpoint

After each surgery, the surgeon completes a user questionnaire. For subjects in the full analysis set, the rate of ‘yes’ responses to the question ***“Did UNITY VCS using vitreoretinal or combined surgical functionality perform per the intended use as defined in protocol Section 5.1?”*** will be presented with a count and percentage and will be accompanied by a two-sided exact binomial 95% confidence interval.

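### The primary 'performed per intended use' rate leaves out eyes aborted after device contact, because its analysis set requires completed surgery

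*SAP*

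**What the plan says.** SAP 2.1 and Protocol 12.2.1 define the full analysis set (FAS) identically: "The full analysis set includes all eyes with successful completion of surgery". The Protocol 3 summary repeats the definition. SAP 4.3 states that "The full analysis set will be used for all effectiveness analysis". Protocol 12.4.1.2 begins the primary analysis with "For subjects in the full analysis set, the rate of" 'yes' responses and attaches a two-sided exact binomial 95% confidence interval; SAP 4.3.1 does the same.

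The safety analysis set (SAP 2.2, Protocol 12.2.2) is wider. It takes in every eye with attempted use, whether the operation was finished or aborted after contact: "Attempted use of the UNITY VCS is defined as any time the device makes contact with the eye". It is assigned to the safety outcomes only.

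On data collection, SAP 4.3.1 says: "After each surgery, the surgeon completes a user questionnaire". Neither document says in terms whether an aborted operation counts as a surgery for this purpose.

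The endpoint in Protocol 6.1 (Table 6-1) is the percentage of 'yes' responses, with no condition that surgery was completed.

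Three other provisions matter. SAP 3 plans a listing "for subjects included in the safety analysis set but excluded from the full analysis set", and conduct summaries for both sets if they differ. Protocol 12.1 adds: "Final subject evaluability must be determined prior to locking the database, based upon the deviations and evaluability plan". Protocol 8.2 removes the data of subjects who become pregnant during the study from the effectiveness analyses.

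**The concern.** Entry to the FAS depends on something that happens after the device is used and is plausibly linked to the answer being measured. If an operation is aborted because the device failed, that eye is the clearest possible 'no', and the set definition takes it out of the primary rate. Neither document plans a rate over all attempted eyes.

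The planned figure therefore answers whether the device performed as intended given that surgery was completed. The endpoint as worded asks about its use without that condition. The study is descriptive (Protocol 12.4.1.1, SAP 4.2), so the estimate and its interval are the whole primary result. Protocol 5.2 says the data are meant to support marketability in Europe, and Protocol 7.2 expects results to be compared with existing evidence. For both uses the denominator matters.

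**Working it through.** **The plan's own figure.** Protocol 12.8 and SAP 7 give the half-width at p = 50% and n = 100 as under 10%. The stated formula gives 1.96 × √(0.5 × 0.5 / 100) = 0.098, or 9.8 points. It reproduces.

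**Inputs.**
- Planned number of surgeries: 100 (Protocol 12.8, SAP 7). I use 100 attempted eyes so that the two denominators are easy to compare.
- Interval: two-sided 95% exact binomial (SAP 4.3.1). For x 'yes' out of n, the lower limit is the 0.025 quantile of Beta(x, n − x + 1), and the upper limit is the 0.975 quantile of Beta(x + 1, n − x). If x = n, the upper limit is 1.
- Number of aborts: not given. All counts below are assumptions, from 0 to 10 per 100.
- 'Yes' rates in completed and aborted eyes: not given, and assumed.

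**Size of the shift.** Let a be the share of attempted eyes that are aborted, c the 'yes' rate in completed eyes and b the 'yes' rate in aborted eyes. The rate in all attempted eyes is (1 − a)c + ab, so

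FAS rate − all-attempted rate = c − [(1 − a)c + ab] = a(c − b).

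The shift is positive if b is below c, zero if a = 0 or b = c, and negative if b is above c.

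**Three aborts in 100 attempts (a = 0.03).**

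| Completed 'yes' | Aborted 'yes' | FAS rate (95% CI) | All-attempted rate (95% CI) | Shift, points |
|---|---|---|---|---|
| 97/97 | 0/3 | 100% (96.3 to 100) | 97/100 = 97.0% (91.5 to 99.4) | 0.03 × (1 − 0) = +3.0 |
| 92/97 | 0/3 | 94.8% (88.4 to 98.3) | 92/100 = 92.0% (84.8 to 96.5) | 0.03 × (0.9485 − 0) = +2.8 |
| 92/97 | 2/3 | 94.8% (88.4 to 98.3) | 94/100 = 94.0% (87.4 to 97.8) | 0.03 × (0.9485 − 0.6667) = +0.8 |
| 92/97 | 3/3 | 94.8% (88.4 to 98.3) | 95/100 = 95.0% (88.7 to 98.4) | 0.03 × (0.9485 − 1) = −0.2 |

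With 3 aborts, +3.0 is the largest possible shift. The −0.2 depends on the assumed 92/97; a lower completed rate with all aborted eyes 'yes' would give a larger negative value.

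**Upper bound by number of aborts (all completed eyes 'yes', all aborted eyes 'no').**

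| Aborted of 100 | FAS (95% CI) | All attempted (95% CI) |
|---|---|---|
| 0 | 100% (96.4 to 100) | 100% (96.4 to 100) |
| 1 | 100% (96.3 to 100) | 99% (94.6 to 100.0) |
| 3 | 100% (96.3 to 100) | 97% (91.5 to 99.4) |
| 5 | 100% (96.2 to 100) | 95% (88.7 to 98.4) |
| 10 | 100% (96.0 to 100) | 90% (82.4 to 95.1) |

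In this case the FAS estimate stays at 100%, and its lower limit moves by only 0.4 points, however many of 0 to 10 operations are aborted.

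**Eyes with no answer.** Assume 97 completed eyes all 'yes' and 3 aborted eyes, two 'no' and one unanswered. The rate on recorded answers is 97/99 = 98.0% (92.9 to 99.8). Counting the unanswered eye as 'no' gives 97/100 = 97.0% (91.5 to 99.4). The gap is small, but it can be seen only if unanswered eyes are counted and reported.

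**The case against.** The population is fixed openly and identically in both documents, so the result is a valid rate conditional on completion. It is too high only relative to a rate over all attempts. That stands, but the endpoint in Protocol 6.1 has no completion condition, so the all-attempts rate is the one its wording describes.

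The effect may be nil. No abort rate is given, the sign can reverse, and a shift of up to about 3 points is modest beside a planning half-width of 9.8 points. There is no test, margin or threshold. All of this stands and limits the weight of the point.

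A reader might infer that device failures vanish from the results. The documents do not support that. A 'no' from any completed operation, including one with a malfunction, stays in the primary rate. Aborted eyes are listed (SAP 3) and enter the adverse event, device deficiency and unplanned procedure outputs (SAP 5.3.1, 5.3.2, 5.3.4). A reader could work out a worst-case rate from the number excluded. These outputs disclose the eyes but leave the primary rate and interval unchanged.

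A reader might also infer that no questionnaire is completed for aborted surgeries. Read plainly, a form after each surgery covers them; parts of the protocol are redacted, and the manual of procedures is not available here. The point needs confirming and is not a demonstrated gap.

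Finally, a reader might take conversion to another system as the only case the set definitions leave open. Read against the safety set, successful most naturally means not aborted, and the deviations and evaluability plan may settle conversions. But it is not the only one: neither set definition reflects the pregnancy exclusion in Protocol 8.2.

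**Conclusion.** The point holds. The primary rate and its interval are conditioned on a post-treatment event linked to the outcome. Measured against the endpoint as worded, the rate is too high whenever aborted eyes have a lower 'yes' rate than completed eyes.

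The size cannot be known from the documents. On an assumed 3 aborts in 100 attempts it runs from about −0.2 to +3.0 points in the cases worked; with no aborts it is zero. No decision rule turns on it. It does not follow that the planned estimate is certain to be inflated or that the study's conclusion would be overturned. It should be fixed because it concerns the only primary performance result and the remedy is small.

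**What to change.** 1. Compute the primary rate and exact 95% interval in all eyes with attempted use of UNITY VCS, which is the existing safety analysis set, using the surgeon's recorded answer. An abort unrelated to the device can then still count as 'yes'.
2. Confirm in writing that the questionnaire is also completed when surgery is aborted. This is best settled while surgeries are under way, since an answer is hard to recover later.
3. Report the FAS rate as supportive.
4. Report the number of attempted eyes with no answer. A row counting them as 'no' is optional and should be labelled as sensitivity only, so that the no-imputation rule (Protocol 12.5, SAP 4.3) still governs the main rate.
5. Make matching edits so that no section contradicts the new primary set: the Protocol 3 summary, Protocol 12.2.1, 12.2.2 and 12.4.1.2, and SAP 2.1, 2.2, 4.3 and 4.3.1.
6. State how the pregnancy exclusion in Protocol 8.2 applies to an endpoint recorded on the day of surgery, given that its stated reason concerns refraction and visual acuity.

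The secondary endpoints can stay as planned.

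The cost is a protocol amendment under Protocol 4, with the approvals that section requires, a matching SAP revision, and one or two extra rows in the primary table. No new data collection is needed if the questionnaire already covers aborted surgeries. The downside for the sponsor is a possibly slightly lower 'yes' rate. A supplementary all-attempted row in the SAP would be lighter, but it would leave the conditional rate as the primary result.
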